4.6 Secondary Outcomes

Secondary outcomes are patient-related outcomes:

- generic functional and specific functional performance, focusing on upper and/or lower extremity and measured by rater observing patients during standardized tests. The tests used will be listed later at point 9.2 by the “Functional independence measurement” (FIM)
- specific functional assessments of the upper AND/OR lower extremity
 - Stroke impact scale (SIS)
- upper extremity:
 - Fugl-Meyer test
 - Box and Block test
- lower extremity:
 - Functional ambulation categories (FAC)
 - Comfortable walking speed (10m Walk test= TMT)
 - Chedoke-McMaster Stroke Assessment Measure (CMSA), the walking index
 - Berg Balance scale (BBS)
- health-related quality of life (EQ-5D)
- **Cost elements** and structures for cost description analysis
 - quantities and prices of inputs (staff, technologies, infrastructure)
 - intensity of use of new rehabilitation technologies
 - h/day, h/week, time of the day
 - description of operational procedures
 - patient(device)/therapist ratio
 - identification of main drivers for increasing efficiency
 - efficiency gains
 - current reimbursement
 - future reimbursement possibilities and models

4.7 Safety Outcomes

Participating patients will be monitored constantly by attending physiotherapists. The ratio of patient to therapist will be between 1:1 and 3:1. Physiotherapists are specially trained in the use of the devices and in life saving measures. Only patients regarded “stable” by their physician to conduct the program will be included.

The subjectively perceived effort by the patient and during the training will be noted on the CRF. Heart rate frequency and blood pressure can be monitored if necessary.

5 STUDY DESIGN AND COURSE OF STUDY

5.1 General Study Design and Justification of the Design

Since the aim of this feasibility study is the development and validation of a new treatment program and not yet, the investigation of effectiveness while controlled with a current state of the art intervention, no control group will be included. A longitudinal single group design has been chosen. Blinding of therapists and patients is accordingly not possible. Blinding of assessment cannot be guaranteed, due to logistical reasons and as assessments are either self-conducted or by attending therapists, who are trained in doing so.

5.2 Study Duration and Study Schedule

The duration of this study is planned to be 30 months (i.e. 2.5 years). The completion depends on the rate of recruitment.

Clinics start recruitment at different dates.

Clinic	Start of recruitment
Klinik Lengg	01.11.2018
Reha Rheinfelden	01.11.2018
Kliniken Valens	01.11.2018
Rehaklinik Zihlschlacht	01.11.2018

Project and study schedule

WP		Project months															
		1	2	3	4	5	6	7	8	9	10	11	12	13	14	15	16
1	Set-up of infrastructure and processes																
2	Patient trainings/-assessments																
3	Analysis/ Dissemination																
4	Communication																
5	Project management																
Milestones	Funding acquired	◆															
	KEK Approval		◆														
	First patient, first visit			◆													
	Interim Analysis				◆												
	Last patient, last visit					◆											
	Final Analysis						◆										

5.3 Methods of Minimizing Bias

Not applicable as no control intervention will be conducted, no randomization and/or blinding for the study design can be applied. Clinics will undertake measures to minimize tester bias.

6 STUDY POPULATION

Four rehabilitation centres located across the German speaking area of Switzerland will participate in this project.

Klinik Lengg, Zurich

The Klinik Lengg has a workload of 250-stroke patients a year. All patients fulfilling the inclusion criteria will be asked for participation.

Reha Rheinfelden

The Reha Rheinfelden has a workload of approximately 400 ischaemic and haemorrhagic stroke patients as in-and outpatients a year, which will be recruited via direct contact, clinic's database, and flyer distributed in-house.

Kliniken Valens

Kliniken Valens treated approximately 460 ischaemic and 150 haemorrhagic stroke inpatients a year, who will be approached by a research assistant to check their eligibility while entering the clinical site for inpatient rehabilitation.

Rehaklinik Zihlschlacht

The Rehaklinik Zihlschlacht has a yearly workload of approximately 300 stroke patients; some of them will be treated after discharge in the clinic's outpatient setting. Study personnel will approach patients regarded eligible for further evaluation.

Each site aims to include five patients leading to 20 patients in total. Study sites are entering the study consecutively and according to their personnel capacity.

6.1 Eligibility Criteria

6.1.1 Inclusion Criteria

Patients fulfilling all of the following inclusion criteria can be enrolled in the study

- Adult patients with residual hemiparesis after cerebrovascular accident
- Up to 12 months after the event
- Primary rehabilitation terminated
- Able to cognitively comprehend the aim of the project
 - At least 22 points in the Montreal Cognitive Assessment (MoCA)
- General health condition allows for intensive rehabilitative training with limited supervision i.e. clearance and prescription of responsible physician
- Understand written and spoken German language

6.1.2 Exclusion Criteria

The presence of any one of the following exclusion criteria will lead to exclusion of the participant:

- Patients with any signs and symptoms showing that the participant is unwilling to participate in the study will result in the patient being excluded from participation
- Any medical condition preventing participation such as

- Severe respiratory disease
- Severe OR unstable cardio-circulatory conditions
- Orthopaedic conditions, especially in extremities targeted for rehabilitation such as
 - fixed joint contractures limiting range of motion
 - non-consolidated fractures
- Neuro-psychological conditions including cognitive deficits limiting communication or non-cooperation like (self-) aggressive behaviour
- Infections or inflammatory diseases, like osteomyelitis
- Specific **absolute contraindication** for the training **with any of the respective devices**:
 - Improper fit of the device, including its harness to relevant extremity(ies)
 - Contraindicated training position (standing, sitting)

Device specific contraindications will be respected and will lead to the exclusion of the device for that patient.

The choice of the device is dependent by the patient's goal, primary impaired limb, and availability at the study site. Comparison of devices is not intended, but to measure the feasibility of their intensive use.

Devices from Hocoma AG Switzerland [HocomaProducts](#)

- Lokomat
- Erigo
- Andago
- Armeo (Boom, Senseo, Spring, Power)
- Valedo Motion

Devices from Tyromotion Austria [Tyromotion](#)

- Amadeo
- Myro

Devices from other manufacturers

- Devices from NuStep: [NuStep](#)
- The Bi-Manu-Trainer by Reha Stim: [Bi-Manu-Trainer](#)
- The EksoGT by Ekso Bionics, USA: [Ekso GT](#)
- The Float by Lutz Medical Engineering, Switzerland: [The Float](#)
- Devices from Reck MOTomed: [MOTomed](#)
- Allegro Medical device by Dynamic devices: [Dynamic Devices](#)

Physicians, not participating in the study, safeguard patient interest and insures proper medical care at every clinical site.

6.2 Recruitment and Screening

Eligible in-and or outpatients attending at each clinic and fulfilling the inclusion criteria will be screened by trained medical personal at each site.

The screening procedure of each participating clinic has been described before (point 6.1).

6.3 Assignment to Study Groups

NA, every patient will be assigned to the intervention under study.

6.4 Criteria for Withdrawal/ Discontinuation of Participants

Patients not willing to adhere to the protocol will not be included. For included patients who, while having already attended some session but are not able to complete the six weeks program within the intensity planned, a tailored reduction of intensity in terms of days, hours per days and/or sessions per day is considered. A maximum training break of 7 days is foreseen

Patients who withdraw before the start of the study will be replaced.

7 STUDY INTERVENTION

7.1 General Information

7.1.1 Study Intervention

- Series of tailored rehabilitative training with the use of new technology which provide feedback and allow for a targeted and intensive and dense training.
- With supervision based on patients preconditions and therapy device (e.g. patient/therapist ratio= 3/1).
- A training series lasts four weeks and comprises 3-5 training-days per week. Maximum training break of 7 days. Five sessions of training with duration of 45 min per session, and up to four hours each day are foreseen.
- The training can take place in an outpatient or inpatient setting.
- Training will be organized in individual one-to-one or group sessions.

7.2 Administration of Study Intervention

7.2.1 Study Intervention

Interventions will be applied and supervised according to the needs, aims and planned interventions (devices used) for each patient individually. Adaptations to a minimum program as outlined under 6.4. can be made.

7.2.2 Control Intervention

n.a.

7.3 Compliance with Intervention

For every patient a CRF including a trainings and intervention plan will be completed. This plan includes measurements to adherence to the intervention plan. The trainings plan will be made in advance and in collaboration by both patient and therapist, including all scheduled days and sessions (devices). Patients not able or willing to fulfil the minimum program outlined before (6.4) will be excluded.

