Study design	Multicenter-single arm feasibility study
Inclusion / Exclusion criteria	
Inclusion:
 
 • Patients with residual hemiparesis after cerebrovascular accident • Up to 12 months after the event • Primary rehabilitation terminated • Able to cognitively comprehend the aim of the project • General health condition allows for intensive rehabilitative training with limited supervision i.e. clearance of responsible physician • Understand written and spoken German language 
Exclusion:
 
 • Presents with contraindication for the training with the respective devices

Study Intervention	
 • Series of tailored rehabilitative trainings with the use of new technology which provide feedback and allow for a targeted, intensive and dense training. • With limited supervision based on patients preconditions and therapy device (e.g. patient/therapist ratio= 3/1). • A training series lasts four weeks and comprises 3-5 training-days per week. Maximum training break of 7 days. A minimum of five blocks of training with duration of 45 min per training day each are foreseen. 
The training can take place in an in- or outpatient setting

Reference Intervention	Not applicable
Number of Participants with Rationale	As this study is a feasibility study: N= 20 (five subjects for every clinical site).
Study Duration	Thirty months (30m) in total.
Study Schedule	11/2018 First-Participant-In (planned) 05/2020 of Last-Participant-Out (planned)
Investigator(s)	
[name] Rehakliniken Zihlschlacht [name] [name] [contact] [contact]
 
[name] Reha Rheinfelden [name] [name] [contact] [contact]
 
[name] Kliniken Valens Rehabilitationszentrum [name] [contact] [contact]
 
[name] Klinik Lengg AG [name] [name] [contact] [contact]

Study Centre(s)	see above

Statistical Considerations	Descriptive analysis Pre-post comparisons of patient-related outcomes
GCP Statement	This study will be conducted in compliance with the protocol, the current version of the Declaration of Helsinki, the ICH-GCP as well as all national legal and regulatory requirements.

LIST OF ABBREVIATIONS

AE	Adverse Event
ClinO	Clinical Trial Ordinance (KlinV)
CRF	Case Report Form
eCRF	Electronic Case Report Form
GCP	Good Clinical Practice
ICH	International Council on Harmonization

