7.4 Data Collection and Follow-up for Withdrawn Participants

Data of all included patients will be analyzed. A follow-up is not planned.

[figure not shown]

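### Section 6.4 gives the wrong programme length and lacks the minimum that 7.2.1 and 7.3 rely on; separately, 10.4 restricts the functional analysis to patients without a long training break

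*Combined protocol and SAP*

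**What the plan says.** **Length.** Section 7.1.1, and the synopsis in the same words, says "A training series lasts four weeks and comprises 3-5 training-days per week". Section 6.4 addresses enrolled patients who "are not able to complete the six weeks program within the intensity planned, a tailored reduction of intensity in terms of days, hours" and so on.

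**Dose and reduction.** The synopsis says "A minimum of five blocks of training with duration of 45 min per training day each are foreseen". Section 7.1.1 has "Five sessions of training with duration of 45 min per session, and up to four hours each day are foreseen", without calling this a minimum. For patients who cannot keep up, 6.4 says that a "tailored reduction of intensity in terms of days, hours per days and/or sessions per day is considered". Apart from the six weeks, the only number in 6.4 is a maximum break of seven days.

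**Minimum programme.** Section 7.2.1 says "Adaptations to a minimum program as outlined under 6.4. can be made". Section 7.3 says "Patients not able or willing to fulfil the minimum program outlined before (6.4) will be excluded". It does not say from what they are excluded: enrolment, further training or analysis.

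**Analysis sets.** Section 7.4 says "Data of all included patients will be analyzed". Section 10.4 puts every patient in the primary analysis, by intention to treat. It then limits the secondary analysis to participants whose training break was seven days or shorter. Under 10.3.2 the secondary analysis contains the pre-post tests of the patient-related outcomes. For patients who stop early, 8.2.4 provides only for asking why. No end assessment is specified for them.

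**The concern.** The trial asks whether patients can sustain an intensive programme. The primary outcome in 4.5 compares planned with performed training days and intensity. The plan therefore needs a clear rule for a patient who starts and cannot keep up.

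The rule as written names a length that the intervention sections do not use, and it depends on a floor that is never stated. Each of the four sites would have to set its own floor, and with five patients per site one or two decisions would show in a site's results.

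The second issue does not depend on the first. The functional results come only from patients who had no long break. If those who broke off for longer also improved less, the mean pre-post change looks better than it was for the enrolled group. A single-arm study has no comparison group that would reveal this.

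**Working it through.** The plan has no power calculation or adherence threshold to reproduce. The check compares sections and adds simple arithmetic.

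**1. Length.** Inputs: 3 to 5 training days per week and five 45-minute sessions per day (synopsis, 7.1.1); four weeks (synopsis, 7.1.1) or six weeks (6.4).
- Four weeks: 4 × 3 = 12 to 4 × 5 = 20 days; × 5 = 60 to 100 sessions; × 45 min = 45 to 75 h.
- Six weeks: 6 × 3 = 18 to 6 × 5 = 30 days; × 5 = 90 to 150 sessions; × 45 min = 67.5 to 112.5 h.
- Ratio 6/4 = 1.5. A patient who completes four full weeks has done 100% of a four-week plan and 4/6 = 67% of a six-week one.

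**2. Is there a minimum programme in 6.4?** It names what may be cut (training days, daily hours, number of sessions) and gives no lower limit for any of them. The seven-day limit concerns breaks, not dose.

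**3. Can another section supply the floor?**
- The synopsis has five blocks per day: 5 × 45 = 225 min. Section 7.1.1 caps the day at four hours, 240 min, and six blocks would take 270 min. Five blocks is thus also the most that fits. If it were the floor, even one session fewer (4 × 45 = 180 min, 80%) would breach it, and the reduction in sessions that 6.4 allows could never be used. It cannot sensibly be the floor that 6.4 intends.
- Three days per week is the lower end of the planned range, but 6.4 allows days to be cut and does not say that three is the limit.

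The references in 7.2.1 and 7.3 therefore point to content that is not there.

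**4. Readings of exclusion in 7.3.**
- Not enrolled: consistent with 7.4 and 10.4, but no rule is left for an enrolled patient who falls below the minimum.
- Taken off training: the site decides when, with no stated floor.
- Left out of the analysis: contradicts 7.4 and the primary set in 10.4.

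**5. Whom does 10.4 remove?** This applies under any reading of 7.3.
- Calendar days in one gap, with a permanent stop counted as a break: over a 28-day series, a last trained day of 20 leaves 28 − 20 = 8 days, so the patient is out. A last trained day of 21 leaves 7, so the patient stays in.
- Missed planned training days: at 5 days per week, out after 12 or fewer of 20 days; at 3 days per week, out after 4 or fewer of 12. A patient planned at 5 days and cut to 3 from the start misses 20 − 12 = 8 days and is also out.

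**6. Effect on functional change.** Suppose that all 20 patients have an end assessment and 10.4 removes k of them. With mean change a in those kept and b in those removed, the overstatement is a − [(20 − k)a + kb]/20 = (k/20)(a − b). The documents give neither k nor a − b. For illustration only, with a − b between 0 and 0.5 SD: k = 2 gives 0 to 0.05 SD, k = 5 gives 0 to 0.125 SD, and k = 10 gives 0 to 0.25 SD. If a = b there is no bias. If those removed improve more, the sign reverses.

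**The case against.** The best defence is that this is a feasibility study of 20 patients with no hypothesis test on adherence and no threshold, and that tailoring is part of the intervention. Six weeks appears only in a withdrawal clause, while the sections that define the intervention agree on four. That is fair: the 50% larger dose in step 1 belongs to a programme that no intervention section prescribes, and a one-word correction removes it. It still has to be made, because the word sits in the rule that sites would apply.

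A reader might infer that 6.4 contradicts the synopsis by allowing cuts below a stated minimum. The documents do not support this. The synopsis gives the planned dose, 6.4 reads as its permitted exception, and 7.3 refers to 6.4 and not to the synopsis. What remains is a reference to a minimum that does not exist.

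A reader might also infer that a site, by stopping a patient under 7.3 rather than reducing the schedule, decides whether that patient enters the functional analysis. That requires exclusion to mean being taken off training, although non-enrolment is at least as natural: the sentence follows one about a plan drawn up beforehand. It also requires a permanent stop to count as a break, and a reduced schedule always to stay within seven days, which step 5 shows is not general.

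Lastly, lower adherence in a patient who stops is a true result, not a bias. Training is recorded each day and reasons for stopping are collected, so reductions would be visible. This stands, and it protects the primary outcome. It does not answer the restriction in 10.4, which is a stated rule and applies whatever the reason for the break.

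**Conclusion.** The point holds on the text. Section 6.4 names six weeks where the programme is four. Sections 7.2.1 and 7.3 depend on a minimum that 6.4 lacks, so the exclusion rule cannot be applied consistently across the four sites. Independently, 10.4 makes the functional pre-post analysis conditional on having no break longer than seven days, which selects on tolerance of the programme.

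The size of any overstatement cannot be calculated from the documents and may be zero. The SD values in step 6 only show how it scales with the number removed and the difference in improvement. The upper figure needs half the sample removed, improving 0.5 SD less than the rest.

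The primary adherence analysis keeps all patients and is not biased by the seven-day rule, and no formal decision depends on it. The point should be fixed because the changes are small and the functional results have no control group behind them.

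**What to change.** - **6.4:** change six weeks to four, and state the minimum programme in days per week and 45-minute sessions per day.
- **7.3:** limit exclusion to non-enrolment when the minimum cannot be planned at baseline. Enrolled patients who reduce or stop remain in the analysis against their baseline CRF plan.
- **10.4:** make the main pre-post analysis all included patients with an end assessment, and keep the seven-day-break set as a supporting analysis.
- **8.2.4:** offer the existing end assessment to patients who stop.

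The cost is wording in these sections and one assessment per patient who stops. Design, sample size and devices stay as they are. Some patients who stop will refuse the assessment, so part of the selection may remain, and the reported functional change may be smaller.

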7.4 Data Collection and Follow-up for Withdrawn Participants

Data of all included patients will be analyzed. A follow-up is not planned.

[figure not shown]
7.5 Concomitant Intervention(s)

All co-interventions such as medication used or other therapies visited during the trial will be recorded.

All concomitant and/or rescue interventions or treatment(s) will be recorded in the CRF.

8 STUDY PROCEDURES

8.1 Study Flow Diagram

8.2 Assessments of Outcomes

8.2.1 Assessment of Primary Outcome (daily)

The primary outcome is to assess the feasibility of planned trainings. Every training and training day will be described in terms of

- device used,
- duration of training
- training mode (passive, active or resistive)
- feedback given

The specific interest is the adherence of the patients

- to planned trainings in terms of planned vs. actually performed training-days and training intensity.
- The subjectively perceived effort by the patients to perform the trainings will be recorded on a visual analogue scale (VAS).
- The subjectively perceived effectiveness will be recorded by using the “Patients Global Impression of Change” = PGICS)

The primary outcomes will be assessed at each intervention day. Either during the training, at the end of each training or at the end of each training day. The PCICS will be assessed at the end of the whole intervention.

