4.5 Primary Outcome

The primary outcome is to assess the feasibility of planned trainings. Every training and training day will be described in terms of

- devices used,
- duration of training,
- training mode (passive, active or resistive) and
- feedback given by the device.

The specific interest is the adherence of the patients:

- to planned trainings in terms of planned vs. actually performed training-days and training intensity.

- the subjectively perceived effort by the patients to perform the trainings will be recorded on a visual analogue scale (VAS).
- the subjectively perceived effectiveness will be recorded by using the “Patients Global Impression of Change” = PGICS)

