8.2.4 Assessments in Participants who prematurely Stop the Study

Project investigators at each site will contact patient who withdrew from the study. Patients will be asked for reasons of withdrawal

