10.4 Handling of Missing Data and Drop-Outs

Primary analysis is according to intention to treat – and all patients will be included.

For secondary analysis, all participants with equal or less than seven days training break of the planned training will be included only.

Analysis of drop-outs will be carried out to find reasons or barriers (CRF) that might explain why sticking to the treatment plan was not possible, whether related or unrelated to the intervention.

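### PGICS, part of the primary outcome, has no planned collection from patients who stop early, although the primary analysis is to include all patients, and section 10.3.1 does not name it

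*Combined protocol and SAP*

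**What the plan says.** Protocol section 4.5 places PGICS within the primary outcome: "the subjectively perceived effectiveness will be recorded by using the" PGICS. Section 8.2.1 repeats this. On timing, 8.2.1 first gives a general rule, "The primary outcomes will be assessed at each intervention day", and then an exception for this one scale (spelled differently there, but evidently the same scale): "The PCICS will be assessed at the end of the whole intervention".

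For patients who stop early, 8.2.4 requires each site to contact them, and the only content it gives is "Patients will be asked for reasons of withdrawal". Section 7.4 commits to analysing the data of all included patients and adds: "A follow-up is not planned".

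Section 10.4 sets the analysis set: "Primary analysis is according to intention to treat – and all patients will be included". Its drop-out analysis looks at why patients could not keep to the plan; it gives no rule for missing outcome values. Section 10.3.1 lists the primary analyses (devices, durations, training and feedback modes, exertion, adherence). PGICS is not among them.

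**The concern.** Adherence and VAS effort are recorded as training proceeds, so a patient who stops in week two still contributes data up to that point. PGICS has a single scheduled time, so the same patient contributes nothing to it. Analysts cannot repair this afterwards, because the rating was never taken.

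This matters because the study asks whether an intensive programme is feasible. Patients who give up bear directly on that question, and their view of whether the training helped is what PGICS would capture. If only completers are rated, a published figure for perceived effectiveness describes those who tolerated the programme, while the stated analysis set leads a reader to assume it describes everyone. With 20 patients, each missing rating is 5 percentage points of the total.

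**Working it through.** **Inputs from the protocol.** Four sites with five patients each (section 10, sample size): 4 × 5 = 20, which reproduces the planned number. No alpha, power, success threshold, drop-out rate or PGICS cut-off for improvement is stated. Patients who withdraw before the start are replaced (6.4); no replacement is described for those who stop later.

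**Step 1: the sections side by side.**
- Is PGICS a primary item? Yes (4.5, 8.2.1).
- When is it taken? Once, at the end (8.2.1).
- Is it taken at early stopping? No section says so. The one contact that exists asks for reasons (8.2.4).
- Who is analysed? All patients (7.4, 10.4).
- How is it summarised, and what happens to missing values? Not stated (10.3.1, 10.4).

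**Step 2: how likely is at least one missing value?** Assume each patient stops early independently with probability d and that no early stopper gives a PGICS. Then P(at least one missing) = 1 − (1 − d)^20, and the expected number of ratings is 20 × (1 − d).
- d = 5%: 64%, 19 ratings
- d = 10%: 88%, 18 ratings
- d = 15%: 96%, 17 ratings
- d = 20%: 99%, 16 ratings
- d = 30%: over 99%, 14 ratings

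The rates are assumed. Over this range, at least one missing value is more likely than not.

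**Step 3: what can then be said about all 20?** Let m patients have no rating and let x of the 20 − m completers report improvement. The completer figure is x/(20 − m). Over all 20 the share lies between x/20 (no early stopper improved) and (x + m)/20 (all did). The width is m/20, whatever x is. With assumed counts:
- m = 2, x = 14: completers 14/18 = 78%; all patients 70% to 80%
- m = 4, x = 12: completers 12/16 = 75%; all patients 60% to 80%
- m = 6, x = 11: completers 11/14 = 79%; all patients 55% to 85%

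**Step 4: direction.** Take m = 4, x = 12, and let k early stoppers have improved. The all-patient share is (12 + k)/20: 60%, 65%, 70%, 75% and 80% for k = 0 to 4. The completer figure of 75% is too high for k = 0, 1 or 2, right for k = 3, and too low for k = 4. It overstates the result only if early stoppers improve less often than completers.

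**Step 5: compare with sampling error.** The exact 95% interval is 48% to 93% for 12/16 and 36% to 81% for 12/20. Sampling uncertainty at this size is wider than the 20-point gap between the bounds. However, an interval computed on completers does not cover the missing-data problem.

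**The case against.** The strongest reply is that the gap may be only in the wording. The timing phrase can be read as each patient's own last training day, and 8.2.4 does not say that nothing else is collected at the contact. The flow diagram under 8.1 and the CRF could not be consulted here and may show an early-stop assessment. This stands in part: the text does not show that early stoppers can never give a PGICS, only that it plans no such collection. A patient who withdraws between sessions would still be reached only through 8.2.4, which does not mention the scale.

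A reader might infer that the plan contradicts its own analysis set. The documents do not support that. Including a patient in an analysis does not promise a value on every item, and early stoppers still contribute their daily data. What is missing is a collection point and a rule for one item.

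A reader might also infer that the result is biased upward. That is not established either. No drop-out rate is given, nothing links stopping to perceived benefit, and 10.4 allows for causes that have nothing to do with the training. Step 4 shows that either direction is possible.

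Two further points reduce the weight. Section 6.4 allows a reduced programme for patients who cannot keep the planned intensity, so some of them may still reach the end and be rated. The study also has no hypothesis or success threshold, so no formal decision depends on PGICS. Neither point supplies the missing denominator: a descriptive percentage still needs one.

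**Conclusion.** The point holds as a gap in planned data collection and analysis for one primary-outcome item. The text schedules no PGICS for patients who stop early, does not name PGICS in the primary analysis, and has no rule for missing ratings, while 10.4 includes everyone. Followed as written, perceived effectiveness would be summarised mainly in completers. It is at risk of bias, probably upward if those who stop are less satisfied.

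The size is unknown. Each missing rating adds 5 percentage points of indeterminacy over 20 patients. In the illustration with four early stoppers, that is 60% to 80% around a completer figure of 75%. This rests on assumed drop-out and improvement counts, on an assumed improved/not improved split that the documents do not define, and on reading 8.2.4 as complete. Adherence and VAS effort are not affected in this way. The change should be made because the rating cannot be recovered later and asking for it is cheap.

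**What to change.** 1. In 8.2.1 and 8.2.4, state that PGICS is also asked at early stopping, using the withdrawal contact already required, and record the date and the number of training days completed by then. Use one spelling for the scale.
2. In 10.3.1, name PGICS as a distribution with all included patients (20 as planned) as denominator. Show three groups separately: completers, early stoppers who answered, and patients without an answer.
3. In 10.4, add one sensitivity line giving the best- and worst-case bounds, with those without an answer counted first as all improved and then as none improved. Define the improved categories in advance.

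The cost is one question at an existing contact, a few table rows and a short protocol edit. Because it changes data collection and the form of analysis, it should go through the amendment route in 2.9. It needs no new visit and no extra patients. The downside is that some early stoppers will not answer, and those who do are rating a partial programme. Their answers should therefore be shown beside those of completers and not pooled with them.
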